5.5 Incentives

All subjects will be rewarded with a present and travel cost will be reimbursed to all participants.

6. ADMINISTRATIVE ASPECTS AND PUBLICATION

6.1 Handling and storage of data and documents

Data will be handled confidentially, subjects will be coded by numbers. Source data will be stored on the secured network of the VUmc and will only be accessible by the principal investigator. The guidelines for data handling and storage from the EMGO Institute of the VUmc will be followed.

6.2 Amendments

Amendments are changes made to the research after a favourable opinion by the accredited METC has been given. All amendments will be notified to the METC that gave a favourable opinion.

6.3 Annual progress report

The sponsor/investigator will submit a summary of the progress of the trial to the accredited METC once a year. Information will be provided on the date of inclusion of the first subject, numbers of subjects included and numbers of subjects that have completed the trial, serious adverse events/ serious adverse reactions, other problems, and amendments.

6.4 End of study report

The investigator will notify the accredited METC of the end of the study within a period of 8 weeks. The end of the study is defined as the last patient's last visit.

In case the study is ended prematurely, the investigator will notify the accredited METC, including the reasons for the premature termination.

Within one year after the end of the study, the investigator/sponsor will submit a final study report with the results of the study, including any publications/abstracts of the study, to the accredited METC.

6.5 Public disclosure and publication policy

Based on the results of this study, at least four articles will be published in scientific journals. Results will also be presented at (inter)national conferences (e.g. International Society for Prosthetics and Orthotics (ISPO) and European Society of Movement Analysis for Adults and Children (ESMAC)).

APPENDIX A. Policy for handling complaints regarding the investigational AFO

When the new AFO is delivered, patients will be instructed to wear the orthosis during an accommodation period. This accommodation period is constructed in a way that the time of wearing the AFO during the day is gradually extended, in order to minimalize the risk of developing problems (e.g. pressure sores). In addition, parents will be instructed to carefully check for pressure sores on the legs or feet of their child and they are instructed to contact the investigator if any problems or complaints occur during the accommodation period.

A standard policy for handling complaints will be followed for each patient (figure 2). Patients will be contacted one week after delivery of each new AFO to check if there are any complaints (adverse events), like pain, discomfort, or pressure sores. If the patient has no complaints, the accommodation period will continue until the next visit is scheduled.

If the patient does experience problems, the investigator will identify these problems and decide which steps need to be taken:

a) For fitting problems like pain or pressure sores, the patient will be directed to the orthotist as soon as possible, in order to adjust the AFO. These fitting problems are common in orthotic care when prescribing a new AFO and can generally be resolved.

b) For gait related problems that are unacceptable for the patient (e.g. frequent falls or extreme fatigue during walking), the investigator will invite the patient to visit the medical center. At the medical center, the investigator will check if any changes in AFO configuration (i.e. neutral angle) can resolve the problem.

After each attempt to resolve a problem, either fitting of gait related, the investigator will contact the patient by phone after several days to check if problems are resolved. If any new problems are present or problems recurred, the investigator will follow the described complaint policy again. For persisting gait-related problems that are unacceptable for the patient, the investigator might decide to end the accommodation period of that AFO configuration and do follow-up measurements immediately. Subsequently, the patient will continue to the next AFO configuration. When problems are resolved, the accommodation period will continue until the next measurement moment is scheduled.

[figure not shown]

Figure 2. Flow-chart of standard policy for handling complaints regarding the investigational AFO. K_1 , K_2 , and K_3 represent either rigid, stiff or flexible stiffness configuration.

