Subjects are asked to keep a motivation diary to note when he/she was (not) wearing his/her AFO during the day and, if applicable, the reason for taking it off. To objectively measure treatment adherence, the adherence-to-treat monitor (@monitor (83)) will be placed into the shaft of the intervention AFO. By measuring temperature differences over time, the @monitor registers whether the AFO is worn or not. The monitor will measure during the last 2 weeks of the follow-up period, simultaneously with the SAM.

Satisfaction

Degree of satisfaction with an AFO will be rated with a scale from 0-10, in which a rate of zero means 'not satisfied at all' and a rate of 10 represents 'complete satisfaction'.

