Baseline measurements with intervention AFO (visit IV, V, and VI)

During the period that the AFO configuration is worn, subjects will also wear the SAM for one week. After wearing the first intervention AFO-FC, subjects will come to the medical center for the evaluation measurements (T1_K). During this visit, 3D-gait analysis and ECWT will be performed, and the FMS and FAQ will be completed. The researcher will ask both the child and parent(s) to rate the worn AFO in terms of satisfaction. Then, properties of the new AFO configuration will be determined and the second AFO-FC will be tuned. Only during visit IV (T1K1), a 3D-gait analysis with the new configuration (K2) will be performed directly,to measure the immediate biomechanical effects of the AFO. The subject will wear the second AFO-FC for four to eight weeks (acclimation period will be matched according to total time that the first AFO-FC is worn), after which the same evaluation measurements will be done (including SAM). The motivation diary will be kept until the next visit to the medical center. This time schedule and set of measurements will be repeated for the third AFO-FC.

Optimal AFO selection (visit VI)

When the short-term follow-up measurements for all AFO configurations are completed, data will be analyzed and the subject's most optimal AFO will be selected. Selection of the subject's optimal AFO will be based on data of gait analysis (primarily on the knee angle in midstance), ECWT, and degree of satisfaction of the child and parent(s). Subsequently, the

Neuro Swing[®] ankle joint system of the subject's AFO-FC will be configured according to what is considered as optimal.

Long-term follow-up measurements (visit VIII)

The subject will wear the optimal AFO-FC during a period of twelve to twenty weeks, to ensure full habitation before long-term follow-up measurements will be performed ($T2_{kopt}$). Measurements at $T2_{kopt}$ will include the CAPE and SAM (of which data will be assessed during the week prior to the visit), adherence (data with the @monitor (83) will be assessed two weeks prior to the visit), 3D-gait analysis, ECWT, FAQ, FMS, and GAS.

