4.2 Adverse and serious adverse events

Adverse events are defined as any undesirable experience occurring to a subject during the study, whether or not considered related to the experimental treatment. All adverse events reported spontaneously by the subject or observed by the investigator or his staff will be recorded.

All serious adverse events (SAEs) will be reported through the web portal *ToetsingOnline* to the accredited METC that approved the protocol, within 15 days after the sponsor has first knowledge of the serious adverse reactions.

SAEs that result in death or are life threatening should be reported expedited. The expedited reporting will occur not later than 7 days after the responsible investigator has first knowledge of the adverse reaction. This is for a preliminary report with another 8 days for completion of the report.

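### No T1 or T2 visit has a specified adverse-event question, so the 11–19 weeks after week 1 of the final optimal-AFO period are never followed by a scheduled enquiry

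*Protocol*

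**What the plan says.** Section 4.2 sets the recording rule: "All adverse events reported spontaneously by the subject or observed by the investigator or his staff will be recorded". Appendix A adds the only enquiry tied to a calendar date: "Patients will be contacted one week after delivery of each new AFO to check if there are any complaints (adverse events"). If nothing is reported at that contact, wear simply continues to the next visit.

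Appendix A also asks families to be alert: "parents will be instructed to carefully check for pressure sores on the legs or feet of their child". Any difficulty noticed while the child is getting used to the AFO should be reported to the investigator. Once someone has tried to fix a problem, "the investigator will contact the patient by phone after several days to check if problems are resolved".

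For the T1 visits, section 3.5.1 says "During this visit, 3D-gait analysis and ECWT will be performed, and the FMS and FAQ will be completed", followed by a satisfaction rating from child and parents. For T2 it lists participation, step activity and adherence data together with "3D-gait analysis, ECWT, FAQ, FMS, and GAS". Neither description, nor Table 2, includes a question about adverse events or complaints. The rating of the AFO itself is a single number: "Degree of satisfaction with an AFO will be rated with a scale from 0-10". Section 3.4.3 also has subjects keep a diary of when the AFO was off and why, but classes it as adherence data.

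**The concern.** The participants are children aged 6 to 14. Appendix A itself names pain, discomfort, pressure sores, frequent falls and extreme fatigue as foreseeable problems. It says that daily wearing time is built up gradually but does not say over how long, so the week-1 contact may come before full daily wear.

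Under the rule in 4.2, whether a later problem is recorded depends on the family raising it or on staff seeing it. A fall some weeks ago or a healed sore cannot be seen at a visit. What gets recorded can therefore differ between children, and between stiffnesses within a child, for reasons unrelated to what happened.

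This matters most in the optimal-AFO period, which is the longest and the last. Section 5.3 only assumes that the new orthosis causes no more pain or burden than a conventional one. A uniform enquiry at the end of each period would let the study report on that assumption.

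**Working it through.** The protocol gives no figure of its own on this point, and the sample-size calculation is not involved. The check is a calendar count.

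**Inputs**
- Wear per test stiffness: 4–8 weeks, three stiffnesses (3.1.1).
- Wear of the optimal AFO: 12–20 weeks (3.1.1 and 3.5.1).
- Scheduled contact: one, at week 1 of each new AFO (Appendix A).
- Planned sample: 32 children (3.2.4).
- Assumption: each of the three stiffness settings counts as a new AFO. Whether the optimal setting does is taken both ways.

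**Test stiffnesses (K1–K3)**
- Weeks after the contact within a period: 4 − 1 = 3 to 8 − 1 = 7.
- The next contact comes one week into the next period, so consecutive enquiries are 3 + 1 = 4 to 7 + 1 = 8 weeks apart. After K3 this needs the contact to cover the optimal AFO, and any time taken to select and set it up is added.
- These weeks are followed by a later enquiry that can look back over them.

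**Optimal AFO**
- If the week-1 contact applies: 12 − 1 = 11 to 20 − 1 = 19 weeks come after it, which is 11/12 = 92% to 19/20 = 95% of the period.
- If it does not apply: all 12–20 weeks, and the weeks after the K3 contact have no later enquiry either.
- T2 is the child's last visit and has no specified question, so no scheduled enquiry ever covers these weeks.

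**With one question at each T1 visit and at T2**
- Scheduled enquiries per child, with the week-1 contact applied to the optimal AFO: now 3 + 1 = 4; then 4 + 3 + 1 = 8. For 32 children: 4 × 32 = 128, then 8 × 32 = 256.
- Optimal-AFO weeks never followed by an enquiry: from 11–19 to 0.
- Interval between the week-1 contact and the next enquiry in that period: still 11–19 weeks. The question at T2 closes the interval; it does not shorten it.

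**Cost**
- 4 added questions × 32 children = 128. At an assumed 3–5 minutes each: 384–640 minutes, or 6.4–10.7 staff hours over the whole study.

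**The case against.** The strongest reply is that silence in a measurement schedule proves little. Table 2 is an overview of tests. The T2 description in 3.5.1 leaves out satisfaction and AFO properties, although Table 2 ticks both at T2, so the lists are not complete even for their own contents. Staff who spend about three hours with a child and parents may well ask about problems. This stands to a degree: the documents show that the question is unspecified, not that nobody will ask it. But an unspecified question is not asked or recorded in a uniform way.

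Second, several channels already run through the later weeks. Parents are told to check and call. Staff watch the child walk. Child and parents rate the AFO. The diary collects reasons for removal, and pain or sores are obvious reasons. This also stands as mitigation. Still, each channel is volunteered, depends on a problem being visible, or is collected for another purpose; the diary is not named as an adverse-event source. For T2 the visit description mentions only the temperature monitor under adherence, so it is not explicit that the diary is kept during the optimal-AFO period.

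Third, risk is probably lower by then. The ankle joint is CE-certified, 5.3 says the children have used AFOs for at least a year, and this orthosis has already been worn for 3 × 4 = 12 to 3 × 8 = 24 weeks. An early contact aimed at fitting problems is a coherent choice. This limits how much the point matters.

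A statistical analysis plan, if one exists, would not normally settle this: what is asked at a visit is a protocol procedure.

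A reader might infer that every week after each week-1 contact goes unexamined, which would be most of the wear time. The documents do not support that, because the later contacts can look back over K1–K3. A reader might also infer that the complaint policy excludes the optimal AFO because the legend to Figure 2 names only K1–K3. That cannot be concluded: the flow chart is not shown, the legend to Figure 1 also spells out only K1–K3 while covering T2, and section 4.3 applies the policy to adverse events generally.

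**Conclusion.** The point holds as a gap in scheduled enquiry at the end of each wear period. It is material only for the optimal AFO, where 11–19 of 12–20 weeks are never followed by a scheduled question. That figure takes the reading more favourable to the protocol, that the week-1 contact covers the reconfigured orthosis; otherwise it is 12–20 weeks.

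These are calendar weeks. They do not estimate missed harm, and nothing in the documents indicates that harm would be missed. Safety is not an endpoint, and no planned efficacy analysis changes. This is a cheap patient-safety improvement and does not affect the validity of the trial's comparisons.

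**What to change.** - Amend 4.2 and 3.5.1 so that one standard question on pain, pressure sores and falls since the last contact is asked and recorded at each of the three T1 visits and at T2.
- At the same visits, review the diary's removal reasons as a source of adverse events, and state that the diary is kept through the optimal-AFO period.
- State in Appendix A that the week-1 contact and the instruction to parents also apply to the optimal AFO.

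I would not add a rule for changing the stiffness during the optimal-AFO period. T2 would then describe a stiffness other than the one selected, which bears on the pre/post comparison in 3.6.3.

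The cost is a short amendment and a few minutes at four existing visits per child, with no added visit. Recorded adverse-event counts will rise because events are asked about, and the report should say so.

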3.1.1 Data collection and study planning

After enrolling the study (recruitment), baseline measurements (T0) will be performed for the subject, walking with shoes only. Additional measurements will be performed for the subject's current AFO (if applicable). Then, for each subject a new AFO will be prescribed, of which stiffness (K) will be varied into three configurations: rigid, stiff, and flexible (further explained in chapter 5). A balanced block randomization will be applied for six possible sequences of AFO stiffness configurations. Each AFO configuration will be worn for an acclimation period of four to eight weeks, after which AFO efficacy will be evaluated (T1_{k1}

 $,T1_{K2}$ and $T1_{K3}$). An analysis the evaluation of all AFO configurations will lead to selection of the stiffness that results in the most favourable effects for a particular subject, referred to as the subject's optimal AFO. This optimal AFO will be worn for twelve to twenty weeks, after which a second set of follow-up measurements ($T2_{Kopt}$) will be done for the selected optimal AFO (figure 1).

Baseline measurements (T0) will have total duration of 4.5 hour. To limit the burden for the subject, baseline testing will be equally sub-divided into three measurement moments: $T0_{cast}$, $T0_{fit}$, and $T0_{deliver}$ (respectively representing the regular consultancies of casting, fitting and delivery of the new AFO).

The evaluation of AFO efficacy will be done for each configuration, and is referred to as $T1_{k1}$, $T1_{K2}$ and $T1_{K3}$ which represent, dependent on the randomization, either a rigid, stiff or flexible configuration. These measurement moments will last approximately three hours each. Subsequent analysis of these measurements will lead to selection of the subject's optimal AFO. Follow-up measurements for the optimal AFO ($T2_{kopt}$) will be done after wearing the orthosis for twelve to twenty weeks. This broad range of long-term follow-up time is included in the study design, since a child's daily activity and participation will be dependent on environmental factors, such as weather circumstances (e.g. temperature). Measurements at $T2_{kopt}$ will have duration of approximately three hours.

Additional (outside lab) measurements will be performed during baseline (T0_{deliver}), evaluation (T1_{κ}) and follow-up (T2_{kopt}) measurements (table 1).

| Measurement moment | | | Location | Duration |

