|--------------------|--------------------------------|-------------------------|-------------|-----------|
| Baseline | Baseline T0 T0 _{cast} | | | 1.5 hours |
| | | TO _{fit} | Lab | 1.5 hours |
| | | T0 _{deliver} | Lab | 1.5 hours |
| | | | Outside lab | 1 week |
| Follow-up | T1 | Τ1 _{K1} | Lab | 3 hours |
| | | | Outside lab | 1 week |
| | | T1 _{K2} | Lab | 3 hours |
| | | | Outside lab | 1 week |
| | | Τ1 _{κ3} | Lab | 3 hours |
| | | | Outside lab | 1 week |
| | T2 | T2 _{kopt} | Lab | 3 hours |
| | | Acpt | Outside lab | 1 week |

| Table 1 | 1. Time | schedule. |
|---------|---------|-----------|
|---------|---------|-----------|

T0=baseline measurements, sub-divided into three measurement moments

T1=follow-up measurements (4-8 weeks) for each AFO configuration

T2=follow-up measurements (12-20 weeks) for the most optimal AFO configuration

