3.4 Study parameters/endpoints

This study will evaluate the efficacy of AFOs in CP, using outcome measures at the ICF components of 'body functions and structures' and 'activities and participation' (45). All measurements are summarized in table 2 and further explained below.

| | | Baseline | | | Follow-up | | |
|-----------------|------------------|-------------------------------|-------------------|------------|-----------------------|-------------------|--------------------|
| | | Bare foot, shoes & old AFO-FC | | New AFO-FC | | | |
| | | T0 _{cast} | T0 _{fit} | | T0 _{deliver} | T1 _k * | T2 _{kopt} |
| | Time interval** | | -2 | +2 | +4-8 | +12- | |
| Primary study p | | | | | | | |
| Activities and | SAM*** | | | | Х | Х | х |
| participation | ECWT | Х | | | | Х | х |
| Secondary stud | ly parameters | | | | | | |
| Body functions | 3D-gait analysis | | | | х | Х | х |
| and structures | Physical fitness | | v | | | | |
| | test | | Х | | | | |
| Activities and | CAPE*** | | | | х | | х |
| participation | CAFE | | | | X | | ~ |
| Other study par | ameters | | | | | | |
| Environmental | Intake | x | | | | | |
| and personal | questionnaire | ^ | | | | | |
| factors | BSS | Х | | | | | |
| | Physical | V | | | | | |
| | examination | Х | | | | | |
| | FAQ | Х | | | | Х | х |
| | FMS | Х | | | | х | х |
| | Gait pattern | Х | | | | | |
| | GAS | Х | | | | | х |
| | GMFCS | Х | | | | | |
| Additional | AFO properties | | Х | | | Х | Х |
| measurements | Adherence | | | | х | х | х |
| | Satisfaction | | | | х | х | х |
| | | | | | | | |

 Table 2. Overview of tests performed at different measurement moments.

 $T1_k$ will be repeated for each AFO-configuration: rigid, stiff, and flexible.

**Time interval represents the number of weeks between measurement moments.

***SAM and CAPE data will be assessed in the week prior to the ticked measurement moment

AFO=Ankle-Foot Orthosis; AFO-FC=AFO footwear combination; BSS='Bronnen van Steun en Spanning'; CAPE=Children's Assessment of Participation and Enjoyment; ECWT=Energy Cost of Walking Test; FAQ=Functional Assessment Questionnaire; FMS=Functional Mobility Scale; GAS=Goal Attainment Scaling; GMFCS=Gross Motor Function Classification System; SAM=StepWatch3TM Activity Monitor.

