3.6 Statistical analysis

All statistical analyses will be done with SPSS.

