3.6.2 Univariate analysis

To analyse differences in AFO efficacy between AFO configurations, means of primary and secondary outcome measures at $T1_{K1}$, $T1_{K2}$, and $T1_{K3}$ will be compared using a repeated measures ANOVA.

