3.6.3 Multivariate analysis

Evaluation of efficacy of the subject's optimal AFO will be based on analyses of pre/postintervention differences in primary and secondary outcome measures. Means of baseline measurements (T0) will be compared to evaluation measurements (T1_K) and long-term follow-up measurements (T2_{Kopt}) using a Linear Mixed Model (LMM) for repeated measures¹.

Multivariate linear regression analyses will be applied to investigate what changes in the secondary outcome measure 'biomechanics of gait' are associated with changes in primary outcome measures 'walking efficiency' and 'daily activity'. First, a stepwise univariate regression (ANOVA) will be performed to determine which factors are significantly associated with changes in biomechanics of gait. Next, significant factors will be analysed in a multivariate regression analysis model.

Multivariate regression analysis will also be applied to investigate to what extent the child characteristics and AFO properties provide determinants for success of treatment with AFOs. First, a stepwise univariate regression (ANOVA) will be performed to determine which factors are significantly associated with outcome of AFO treatment. Significant factors will be inculded in a multivariate regression model. Factors that will be analysed in the model will include baseline motor impairements, GMFCS level, gait pattern, EC of walking, physical fitness level, and AFO stiffness and neutral anlge.

¹ Participation measures (assessed with the CAPE) will only be done at baseline (T0) and at long-term follow-up (T2). Assuming that data are normally distributed, means of this outcome measure will be compared using paired samples t-test.

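### The stiffness comparison uses a repeated measures ANOVA that usually drops any child without all three T1 values; the mixed model already named in section 3.6.3 would keep them (minor, cheap improvement)

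*Protocol*

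**What the plan says.** Section 3.6.2 states that the means of the primary and secondary outcomes at the three T1 visits "will be compared using a repeated measures ANOVA". Section 3.6 adds "All statistical analyses will be done with SPSS". Section 3.6.3 evaluates T0 against T1 and T2 "using a Linear Mixed Model (LMM) for repeated measures", but does not extend that model to the comparison between configurations.

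Two provisions can leave a child with fewer than three T1 values.

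- Section 3.5.3 says that children who withdraw are not replaced.
- Appendix A deals with gait problems that persist and that the child cannot accept. In that case "the investigator might decide to end the accommodation period of that AFO configuration and do follow-up measurements immediately", and the child moves on to the next configuration.

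The timing of the SAM week, which supplies one of the two primary outcomes, is described in more than one way. The Table 2 footnote says "SAM and CAPE data will be assessed in the week prior to the ticked measurement moment". Section 3.5.1 says only "During the period that the AFO configuration is worn, subjects will also wear the SAM for one week". Table 1 lists "Outside lab | 1 week" beside the lab part of every T1 visit. The Appendix A flow chart (Figure 2) is not available in the text at hand.

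**The concern.** A classical repeated measures ANOVA, as usually run in SPSS, needs one row per child with every level filled. If one of the three values is missing, the other two leave the analysis although they are valid.

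The protocol itself creates two routes to this. A child who withdraws after two configurations loses the third value of both primary outcomes. A child whose configuration is ended early still has energy cost and gait measured at the immediate visit, possibly after less than the planned 4 to 8 weeks of wear, but may have no complete SAM week for that configuration.

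What is at stake is some precision in the stiffness comparison. Possibly the set of children analysed is also tilted away from those who tolerated one stiffness badly. The protocol already names a model that would keep these values.

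**Working it through.** **1. The plan's own figure.** Section 3.2.4 gives SD 1.70, difference 1.26, power 80% and alpha 0.05 (two-sided reproduces). N = 2 × 1.70² × (1.960 + 0.842)² / 1.26² = 28.58, rounded up to 29, as stated. The 32 planned children leave a margin of 3, meant partly for dropout and partly for the regression. This figure concerns energy cost and does not change. It serves here only to set a range.

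**2. Assumption.** No early-stop or withdrawal rate is given. Let k be the number of children with one T1 value missing and two present; take k = 1 to 3 of 32.

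**3. Values discarded.** Of 96 planned values per outcome, 96 − k are observed. The complete-case ANOVA uses 3 × (32 − k) and so discards 2k valid values.
- k = 1: 95 observed, 93 used, 2 discarded.
- k = 3: 93 observed, 87 used, 6 discarded.

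**4. Precision.** Assume equal correlation ρ between a child's three values (0.5 to 0.9), treated as known. Compare the variance of a contrast from complete cases with that from all available data.

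- All k losses on one stiffness, contrast of the two other levels: the ratio is 32 / (32 − k). For k = 1 it is 32/31 = 1.032, square root 1.016. For k = 3 it is 32/29 = 1.103, square root 1.050. Intervals are therefore about 2% or 5% wider. This is the largest effect.
- Same pattern, contrasts that involve the affected level: the ratio is 1 / (1 − f × k/32) with f = 1 / (2(1 + ρ)), so f = 0.333 at ρ = 0.5 and 0.263 at ρ = 0.9. For k = 1 the ratio is 1.008 to 1.011. For k = 3 it is 1.025 to 1.032.
- k = 3 spread evenly, one loss per stiffness: every contrast has a ratio of 1.053 to 1.057, so intervals are about 3% wider (√1.057 = 1.028). Withdrawals should lie nearer to this case, because wear order is balanced by block randomization.
- With period as a fixed effect in both models, the largest ratios are 1.033 (k = 1) and 1.107 (k = 3), so the result does not depend on period adjustment.

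A child who leaves after only one configuration has a single value, which adds little to a within-child contrast in either analysis.

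**5. When a SAM week could be lost.** On the Table 2 timing, a visit planned for week W has its SAM week from W − 1 to W. If that planned week is not moved, a stop before week 3 (W = 4) or week 7 (W = 8) yields no SAM days. Appendix A has the first routine complaint call one week after delivery and re-checks several days after each attempted remedy, so a stop that early is possible. On the wording of section 3.5.1 and Table 1, the week could still be obtained.

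**6. Bias.** An illustrative simulation (300 runs per setting, ρ = 0.7, true contrast of affected against unaffected level −0.30 SD) made less active children more likely to miss one stiffness. With about 10% missing (3 of 32), the contrast was −0.31 from complete cases and −0.29 from the mixed model, no clear shift. With about 20% missing (6 of 32), it was −0.35 against −0.31. The contrast of the two unaffected levels stayed at about zero in both. The mechanism is assumed, so this shows what could happen, not what will.

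**The case against.** The best reply is that both losses are inferred. Appendix A speaks of follow-up measurements in general, and Table 1 counts a one-week outside-lab part as belonging to each T1. A reader might infer that an early stop necessarily costs the SAM week. The documents do not support that: it is one of two readings, and the flow chart for this situation cannot be seen. This part of the objection stands. Withdrawal, however, produces incomplete sets on either reading. Nor does section 3.6.2 specify a complete-case set, and handling of missing data may properly sit in an analysis plan that is not shown. But the choice of ANOVA is fixed in the protocol, and its usual form has this property.

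It is also fair that little hangs on this comparison for daily activity. No research question asks for SAM by stiffness level. Question 2a concerns gait. Selection of the optimal AFO uses gait, energy cost and satisfaction. The section 3.6.3 mixed model keeps the child's other values for the pre/post question. A reader might infer that the main efficacy result is weakened; it is not.

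Two stronger readings on size also fail. With 6 of 32 children affected, the largest effect would be intervals 11% wider (√(32/26) = 1.109), but nothing supports that rate: a stop requires a problem that persists after attempted correction. In the 20% simulation, the mean of a fully observed stiffness shifted by about 0.2 SD under complete cases. That is a shift in a mean, under an assumed mechanism, not in the within-child contrast that the ANOVA tests, where stable differences between children cancel.

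**Conclusion.** The point holds as a minor, inexpensive improvement. The protocol fixes an analysis that usually discards valid T1 values, while its own rules make incomplete sets foreseeable and it already names a method that would keep them. The consequence is confined to the stiffness comparison. It affects both primary outcomes through withdrawal, and daily activity alone through an early stop if the Table 2 timing is followed.

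For 1 to 3 affected children, the largest widening of any interval is about 2% to 5%, and most contrasts lose less. This rests on an assumed rate, equal correlations of 0.5 to 0.9 and one missing value per child. Bias in the within-child contrast is possible, because early stops are linked to poor tolerance, but it is not shown and cannot be sized from the document.

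**What to change.** In section 3.6.2, replace the repeated measures ANOVA with the linear mixed model of section 3.6.3: stiffness level and period as fixed effects, child as random effect, all available T1 values. Name stiffness level explicitly, because K1 to K3 denote the order of wear (section 3.1.1). Include period because three wear periods of 4 to 8 weeks span 12 to 24 weeks. Block randomization already balances order by design, so this is a refinement, not a repair.

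Add one sensitivity analysis without T1 values taken before 4 weeks of wear, since energy cost and gait at an early stop come from a shorter acclimation than planned.

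Leave the Appendix A safety stop unchanged. I would not ask for the SAM to be issued at a complaint visit: days from a failing configuration, perhaps worn for only part of the day, are not fully comparable with an acclimated week.

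The cost is a sentence of text and slightly more analysis in the same software, with no extra visit. The mixed model does not remove bias if a missing value depends on what it would have been.
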